4 ANALYSIS POPULATIONS

4.1 Intent-to-treat Population

The intent-to-treat (ITT) population will include all randomized subjects.

4.2 Safety Population

The safety population includes all subjects who received any amount of study drug treatment and will be the population for safety evaluations.

4.3 Full Analysis Population

The full analysis set (FAS) or population is a subset of the ITT set from which subjects are excluded who did not receive any study drug or have a baseline aggregate five symptom score of >5. For the secondary analyses of individual symptom scores and quality-of-life responses, further subjects who do not have a baseline score of >1 for that symptom or response will be excluded.

4.4 Per-Protocol Population

The per-protocol (PP) set, defined as subjects who do not have a major protocol deviation prior to resolution of the aggregated five symptoms, will also be used as supportive evidence of efficacy. Subjects who are non-compliant with the requirements of the protocol after achieving resolution of the five COVID-19 symptoms will be included in the PP set due to the expectation that such subjects will likely discontinue prematurely from the study.

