9.5 Analysis Populations

The intent-to-treat (ITT) population will include all randomized subjects.

The full analysis set (FAS) or population is a subset of the ITT set from which subjects are excluded who did not receive any study drug or have a baseline aggregate five symptom score of ≤ 5 . For the secondary analyses of individual symptom scores and quality-of-life responses, further subjects who do not have a baseline score of >1 for that symptom or response will be excluded.

A PP population, defined as subjects who do not have a major protocol deviation prior to resolution of the aggregated five symptoms, will also be used as supportive evidence of efficacy. Subjects who are non-compliant with the requirements of the protocol after achieving resolution of the five COVID-19 symptoms will be included in the PP set due to the expectation that such subjects will likely discontinue prematurely from the study.

The safety population includes all subjects who received any amount of study treatment and will be the population for safety evaluations.

For each analysis population, baseline subject characteristics, including age, sex, race, ethnicity, height, weight, BMI and eGFR will be summarized by study arm (CTAP101 Capsules and placebo). Primary, secondary **methods** outcomes will be summarized by study arm and FU time points, using CONSORT guidelines to present descriptive statistics, including mean, median, standard deviation, quartiles, interquartile range, minimum, and maximum values for subjects within the site, overall and by treatment group. Continuous variables will be summarized using means, standard deviations, and quartiles, while categorical variables will be summarized using frequencies and percentages.

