4.5 Protocol Deviations

Protocol deviations are any intentional or unintentional changes from an Investigational Review Board (IRB) approved protocol that are not approved by the IRB prior to initiation of the change. All known protocol deviations are collected by electronic data capture (EDC). Major protocol deviations are deviations that result in increased risk to subjects, affect the rights, safety, or welfare of the subjects or affect the integrity of the study. Major protocol deviations may include, but are not limited to, deviations from the inclusion/exclusion criteria, informed consent deviations, concomitant medication restrictions, and any other protocol requirement that results in a significant, added risk to the subject or has an impact on the quality of the data collected or the outcome of the study. Detailed definitions of major protocol deviations are delineated in the "CTAP101-CL-2014 Study Protocol Deviation Plan." Upon completion of the study, any subject with a major protocol deviation prior to resolution of the aggregated five symptoms will be excluded from the PP population. All protocol deviations will be presented in by-subject listings, and subjects excluded from the PP population will be documented before database lock.

ENDPOINTS 5

5.1 **Primary Safety Endpoints**

The safety and tolerability of Rayaldee (CTAP101 Capsules) will be evaluated using the following assessments:

- Adverse Events;
- Physical Examinations;
- Vital Signs;
- Electrocardiograms; and,
- Hematology and Clinical Chemistries.

Special attention will be given to changes in serum total calcium (corrected for serum albumin), serum phosphorus, and estimated glomerular filtration rate (eGFR).

5.2 **Primary Efficacy Endpoints**

The primary efficacy endpoints are:

- 1. Attainment of serum total 25D levels ≥50 ng/mL, as assessed at Day 14.

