6.10 Efficacy Analyses

6.10.1 Primary Efficacy Endpoints

The two primary efficacy endpoints will be tested hierarchically to maintain an overall one-sided alpha level of 0.025. Therefore, the test of resolution of symptoms based on the aggregate FLU-PRO Plus[©] symptom score will be performed only if the attainment of serum 25D levels \geq 50 ng/mL at Day 14 is significant at <0.025.

The first primary efficacy endpoint, attainment of serum 25D levels at ≥50 ng/mL, will be assessed with a Chi-square statistic at Day 14. The serum 25D levels will also be compared between treatment groups at Days 7, 21 and 28 with a Chi-square statistic.

The second primary efficacy endpoint is the number of days to resolution of symptoms, defined as a reduction in the aggregate FLU-PRO Plus[©] score for the selected five COVID-19 symptoms recorded on Day 0 (prior to study drug initiation) to or below 5 for a minimum of three consecutive days. The time to resolution is defined as the number of days from Day 1 (study drug initiation) to the first day of achieving the aggregate ≤5 score for a minimum of three consecutive days, provided that no score greater than 5 is recorded between the two qualifying scores. Resolution will be determined by the first two successive qualifying scores which span a minimum of three consecutive days. For clarity, resolution will be considered as having been achieved if two successive aggregate scores of ≤5 are recorded on the first day of this occurrence and on a subsequent day that is at least two days (but not more than 5 days) later even if no score has been recorded between the two days. Missing symptom score values will be handled as described in Section 6.2. The number of days to resolution will be analyzed with a Cox proportional hazards model with covariates (baseline aggregate FLU-PRO Plus[©] score for the selected five COVID-19 symptoms, baseline serum 25D, and body weight).

As a sensitivity analysis of the resolution of symptoms, a tipping point approach will be used starting with the analysis in which scores are available for three consecutive days, with no missing interval, followed by increasing numbers of missing days in the up to five-day interval, that is, 1, 2 and 3 missing days between the two consecutive qualifying scores.

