8 TABLES, LISTINGS AND FIGURES

8.1 List of Tables

The Tables to be generated include, but not limited to the following:

CONDUCT OF STUDY

14.1.1	Disposition of Subjects: All Enrolled Subjects
14.1.1.1	Major Protocol Deviations: Full Analysis Population
14.1.2.1	Demographics and Baseline Characteristics: Intent-to-Treat Population
14.1.2.2	Demographics and Baseline Characteristics: Full Analysis Population
14.1.2.3	Demographics and Baseline Characteristics: Per Protocol Population
14.1.2.4	Demographics and Baseline Characteristics: Safety Population
14.1.3	Prior and Concomitant Medications by ATC Level 2 and Preferred Term: Safety
	Population

PRIMARY EFFICACY ENDPOINTS

[figure not shown]
14.2.1.1	Attainment of Serum 25D Levels >=50 ng/mL by Visit: Full Analysis Population
14.2.1.2	Attainment of Serum 25D Levels >=50 ng/mL by Visit: Per Protocol Population
14.2.1.3	Attainment of Serum 25D Levels >=50 ng/mL by Visit and by Subgroups: Full
	Analysis Population
14.2.1.4	Attainment of Serum 25D Levels >=50 ng/mL by Visit and by Subgroups: Per
	Protocol Population
14.2.1.5	Time to Resolution of COVID-19 Symptoms Based on FLU-PRO Plus COVID-
	19 Five Symptom Aggregate Score: Full Analysis Population
14.2.1.6	Time to Resolution of COVID-19 Symptoms Based on FLU-PRO Plus COVID-
	19 Five Symptom Aggregate Score: Per Protocol Population
14.2.1.7	Time to Resolution of COVID-19 Symptoms Based on FLU-PRO Plus COVID-
	19 Five Symptom Aggregate Score - Cox Proportional Hazards Model Summary
	of Effects: Full Analysis Population
14.2.1.8	Time to Resolution of COVID-19 Symptoms Based on FLU-PRO Plus COVID-
	19 Five Symptom Aggregate Score - Cox Proportional Hazards Model Summary
	of Effects: Per Protocol Population
14.2.1.9	Tipping Point Analysis for Time to Resolution of COVID-19 Symptoms Based
	on FLU-PRO Plus COVID-19 Five Symptom Aggregate Score: Full Analysis
	Population
14.2.1.10	Tipping Point Analysis for Time to Resolution of COVID-19 Symptoms Based
	on FLU-PRO Plus COVID-19 Five Symptom Aggregate Score: Per Protocol
	Population
14.2.1.11	Time to Resolution of COVID-19 Symptoms Based on FLU-PRO Plus COVID-
	19 Five Symptom Aggregate Score by Subgroups: Full Analysis Population
14.2.1.12	Time to Resolution of COVID-19 Symptoms Based on FLU-PRO Plus COVID-
	19 Five Symptom Aggregate Score by Subgroups: Per Protocol Population

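### Per-protocol membership depends on whether resolution came before a major deviation, so the supportive hazard ratio can be biased when post-baseline deviation rates differ by arm

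*SAP*

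**What the plan says.** Three places give the same rule. SAP 4.4 defines the PP set as "subjects who do not have a major protocol deviation prior to resolution of the aggregated five symptoms", and Protocol 9.5 matches it: "defined as subjects who do not have a major protocol deviation prior to resolution of the aggregated five symptoms". SAP 4.5 makes clear that the whole subject is removed: "any subject with a major protocol deviation prior to resolution of the aggregated five symptoms will be excluded from the PP population". The other half of the rule is in SAP 4.4: "Subjects who are non-compliant with the requirements of the protocol after achieving resolution of the five COVID-19 symptoms will be included in the PP" set.

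The role of the set is that it "will also be used as supportive evidence of efficacy". For the second primary endpoint, SAP 6.10.1 states: "The number of days to resolution will be analyzed with a Cox proportional hazards model with covariates". That model is repeated in the PP set as Table 14.2.1.8 in SAP 8.1. Attainment of 25D by visit is also reported in the PP set (Table 14.2.1.2), as are nearly all the primary and secondary efficacy tables. Neither document censors at a deviation or limits PP exclusions to deviations present at entry.

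**The concern.** Take two subjects with the same major deviation on the same day. One has already resolved and stays in the PP set. The other is still symptomatic and is removed with all of his or her follow-up. Membership therefore depends on the event being analysed. A slow resolver is exposed to exclusion for longer than a fast one, so exclusion falls mainly on slow resolvers.

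Two consequences follow. The PP proportion resolved is too high in any arm that has post-baseline deviations. If one arm has more such deviations, it loses more of its slow resolvers and its PP result improves relative to the other arm. An analysis meant to support the FAS result could then show a benefit where there is none, or shrink a real one.

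The rule also fits the first primary endpoint poorly. A subject who resolves on Day 5 and then departs from the protocol still counts as per protocol for 25D at Days 14, 21 and 28. A subject with the same departure who is still symptomatic is excluded if the departure is classed as major. Whether symptoms have resolved says nothing about exposure to the drug.

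**Working it through.** **The plan's own figures.** The documents state no figure for the PP set, so the design assumptions in SAP 3.3 are the base. With 50% and 70% resolved by Day 28 and constant hazards, HR = ln(0.30)/ln(0.50) = 1.737, which reproduces 1.74. With follow-up to Day 42 (Protocol 3.5) and 80 per arm, 118.6 events are expected, and the Schoenfeld formula gives 85.4% power, consistent with the stated figure of more than 80%. (At Day 28 there are 80 × 0.5 + 80 × 0.7 = 96 events and 77.4%; that is a separate matter.)

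**Assumptions.** The documents give no deviation rate. Time to the first post-baseline major deviation is taken as exponential, independent of resolution, with 10% to 30% of an arm deviating by Day 28. Two windows are used: deviations stop at Day 28, since dosing ends on Day 27, or they continue to Day 42.

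**Step 1: inflation within one arm, in closed form.** Take the placebo assumption (50% resolved by Day 28) and 20% deviating by Day 28.
- Share of first events that are resolutions: ln 2 / (ln 2 − ln 0.8) = 0.6931/0.9163 = 0.7565.
- Resolved by Day 28 before any deviation: 0.7565 × (1 − 0.5 × 0.8) = 0.454.
- Retained if deviations stop at Day 28: 0.454 + 0.5 × 0.8 = 0.854. PP proportion resolved by Day 28: 0.454/0.854 = 53%.
- Retained if deviations continue to Day 42: 0.7565 × (1 − 0.4^1.5) + 0.4^1.5 = 0.565 + 0.253 = 0.818. PP proportion resolved by Day 28: 0.454/0.818 = 55.5%.

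The true figure is 50%. No difference between arms is needed for this.

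**Step 2: effect on the HR, by simulation.** Resolution times are exponential, with an unadjusted Cox model and follow-up to Day 42. HRs for deviations continuing to Day 42 come mainly from 300,000 subjects per arm, with error rates from 6,000 trials of 80 per arm. The Day 28 window used 4,000 trials. Ranges within a cell show the spread across separate runs.

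| Deviating by Day 28, placebo v active | True HR | PP HR, stop at Day 28 | PP HR, continue to Day 42 | One-sided error, stop / continue |
|---|---|---|---|---|
| 20% v 20% | 1.00 | 1.00 | 1.00 | 2–3% / 2–3% |
| 20% v 20% | 1.74 | 1.71 | 1.69 | – |
| 10% v 20% | 1.00 | 1.04 | 1.08 | 4% / 6% |
| 10% v 30% | 1.00 | 1.09 | 1.16–1.19 | 6% / 11–14% |
| 30% v 10% | 1.00 | 0.92 | 0.85 | – |
| 30% v 10% | 1.74 | 1.58 | 1.45 | – |

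In the 10% v 30% row, the largest run gave HR 1.16 and error 10.8%; 1.19 and 14% are the highest values seen.

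**Step 3: the alternative.** Keeping every subject and censoring at the first post-baseline deviation gave an HR of 0.99 to 1.00 under the null and 1.72 to 1.74 under the design alternative. It matched the all-subject HR to within 0.005 throughout, with error of 2.4% to 2.9%. When deviation was also made to depend on prognosis, the null HR under censoring was 0.98 to 1.01; in the same runs with unequal rates the PP rule gave 0.92 and 1.09.

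**Step 4: what is not affected.** A deviation present at entry precedes resolution for everyone, so excluding for it does not depend on the event. A deviation after resolution cannot change the resolution time, so ignoring it is sound for that endpoint. The fault lies only in removing the whole subject for a deviation between baseline and resolution.

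**The case against.** The strongest reply is that the harm is conditional and confined to a secondary role. The PP analysis carries no alpha, FAS tables accompany it, and SAP 4.5 requires exclusions to be documented before database lock. All of that stands. Documentation before lock limits discretion but does not remove the dependence on outcome.

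A reader might infer that the PP HR is biased as it stands. The documents do not support that. With equal deviation rates the null HR is 1.00, and 1.74 shrinks only to about 1.69 to 1.71 at 20%. A material bias needs rates that differ by arm, and no rate is given.

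A reader might also expect dose changes or drug withdrawal to create the imbalance. Protocol 5.3.1, 5.3.2 and 6.9 provide for these, so following them is not a deviation. Of the examples of major deviations in SAP 4.5, eligibility and consent arise at entry. The trial is double-blind with on-treatment 25D concealed (Protocol 5.12), and Protocol 1.5 reports mostly comparable adverse events between arms in earlier studies. The detailed definitions are in a separate deviation plan that is not available here, so a gap of 10% v 30% is an extreme case and not a documented expectation.

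Finally, an error rate above 2.5% in the PP set might be read as inflating the trial's error. It does not, because the PP set is outside the hierarchy in SAP 6.10.1.

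**Conclusion.** The concern holds in a conditional form. As defined, PP membership depends on the event being analysed, and slow resolvers are removed selectively. PP proportions resolved are too favourable even with balanced deviations: at 20% deviating, 50% resolved becomes 53% to 55.5%. The PP HR can be biased in either direction when post-baseline deviation rates differ by arm. With a twofold difference the distortion is modest; with a threefold difference it is large enough to mislead in either direction.

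Confidence is high in the mechanism and low in the size. The size rests on assumed deviation rates, exponential times and the window over which deviations can occur, and the figures fall by nearly half if deviations stop at Day 28. The primary FAS test and the alpha hierarchy are untouched. The change is worth making because the PP tables are meant to corroborate the FAS result, and a simple redefinition lets them do so.

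**What to change.** Replace the PP rule in SAP 4.4 and 4.5 with two definitions that do not refer to symptom resolution.

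- **Time to resolution:** exclude only subjects with a major deviation present at entry, for example in eligibility or consent. Keep subjects whose first major deviation comes later, and censor them at its date if they have not yet resolved. Deviations after resolution then have no effect, as now.
- **25D at Day 14:** define membership by major deviations up to the Day 14 sample, whether or not symptoms have resolved.

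State which rule applies to each PP table in SAP 8.1.

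The cost is one SAP paragraph and the date of the first major deviation in the analysis dataset; deviations are already collected in EDC. SAP 1 says that the SAP supersedes the protocol on analyses, so the text in Protocol 9.5 need not hold this up. The small downside is that censoring assumes the deviation is not itself driven by prognosis; the SAP should say so. In the one dependent case tried, the resulting error in the HR was about 2% at most.

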4.5 Protocol Deviations

Protocol deviations are any intentional or unintentional changes from an Investigational Review Board (IRB) approved protocol that are not approved by the IRB prior to initiation of the change. All known protocol deviations are collected by electronic data capture (EDC). Major protocol deviations are deviations that result in increased risk to subjects, affect the rights, safety, or welfare of the subjects or affect the integrity of the study. Major protocol deviations may include, but are not limited to, deviations from the inclusion/exclusion criteria, informed consent deviations, concomitant medication restrictions, and any other protocol requirement that results in a significant, added risk to the subject or has an impact on the quality of the data collected or the outcome of the study. Detailed definitions of major protocol deviations are delineated in the "CTAP101-CL-2014 Study Protocol Deviation Plan." Upon completion of the study, any subject with a major protocol deviation prior to resolution of the aggregated five symptoms will be excluded from the PP population. All protocol deviations will be presented in by-subject listings, and subjects excluded from the PP population will be documented before database lock.

ENDPOINTS 5

5.1 **Primary Safety Endpoints**

The safety and tolerability of Rayaldee (CTAP101 Capsules) will be evaluated using the following assessments:

- Adverse Events;
- Physical Examinations;
- Vital Signs;
- Electrocardiograms; and,
- Hematology and Clinical Chemistries.

Special attention will be given to changes in serum total calcium (corrected for serum albumin), serum phosphorus, and estimated glomerular filtration rate (eGFR).

5.2 **Primary Efficacy Endpoints**

The primary efficacy endpoints are:

- 1. Attainment of serum total 25D levels ≥50 ng/mL, as assessed at Day 14.
- 2. The number of days to resolution of the selected five COVID-19 symptoms (trouble breathing, chest congestion, dry or hacking cough, body aches and pains, and chills and shivering), defined as a reduction in the aggregate symptom score recorded on Day 0 (prior to study drug initiation) by the FLU-PRO Plus[©] questionnaire to or below 5 for a minimum of three consecutive days. These five symptoms are part of the chest/respiratory and body/systemic domains of the FLU-PRO Plus[©] questionnaire for which average scores of ≥1.5 were required for each domain for inclusion in the study. Trouble breathing, chest congestion and dry or hacking cough are symptoms indicative of potentially inadequate oxygenation and an impending requirement for supplemental oxygen and hospitalization. Body aches and pains and chills and shivering are symptoms indicative of systemic inflammatory responses associated with active viral infection. Resolution of each of these five symptoms will be analyzed separately, as well, as secondary efficacy endpoints. An aggregate score for the primary efficacy endpoint related to the selected five COVID-19 symptoms is deemed appropriate in view of the observed heterogeneity in COVID-19 symptom profiles. Not all subjects experience the same symptoms or degree of symptom severity. For example, some subjects experience trouble breathing but are free of dry or

hacking cough. Others have no difficulty breathing but report chest congestion or coughing. This situation supports an argument against focusing on one or two symptoms, as a significant number of subjects may not have experienced those symptoms. It also supports an argument to use an aggregate score, since consideration of a larger number of symptoms makes the endpoint applicable to a larger number of subjects. Based on analysis of blinded data obtained from the study, more than 92% of subjects who received at least one dose of study drug had an aggregate symptom score higher than 5 at baseline (Day 0). The main reason why a few subjects do not have an aggregate baseline score higher than 5 is that they get well rather quickly, even before starting study drug. Such subjects will be excluded from the FAS.

The time to resolution is defined as the number of days from Day 1 (study drug initiation) to the first day of achieving the ≤ 5 score for a minimum of three consecutive days. The number of days to resolution will be determined by the first two successive qualifying scores which span a minimum of three consecutive days, provided that no score greater than 5 is recorded between the two qualifying scores. For clarity, resolution will be considered as having been achieved if two successive aggregate scores of ≤ 5 are recorded on the first day of this period and on a subsequent day that is at least two days (but not longer than 5 days) later even if no score has been recorded between the two days.

On each day during the study, subjects will record once daily (during a 24-hour period starting in the evening before the subject goes to sleep) the severity of COVID-19 symptoms using the FLU-PRO Plus[©] questionnaire.

[figure not shown]
5.3 Secondary Efficacy Endpoints

The secondary endpoints are:

- 1. The number of days to resolution of five symptoms (trouble breathing, chest congestion, dry or hacking cough, body aches and pains, and chills and shivering), as measured by the FLU-PRO Plus[©] questionnaire, with resolution defined as the first aggregate symptom score of ≤5 which is maintained for a minimum of three consecutive days, with no individual symptom score >1:
- 2. Resolution, defined as the first score of ≤5 which is maintained for a minimum of three consecutive days (without subsequent relapse), for the aggregate five COVID-19 symptoms (trouble breathing, chest congestion, dry or hacking cough, body aches and pains, and chills and shivering) and for each individual symptom, defined as a score of 0 or 1, as measured by the FLU-PRO Plus[©] questionnaire as of Day 10;
- 3. Incidence of emergency room/urgent care visits;
- 4. Incidence of oxygen saturation below 94% (or requirement for supplemental oxygen);
- 5. Incidence and duration of hospitalizations;
- 6. Incidence of requirement for mechanical ventilation;
- 7. Mortality rate (as incidence);
- 8. Severity and duration of COVID-19 illness as evidenced by quality-of-life measures including ability to perform usual activities and opinion of overall health status, using the FLU-PRO Plus[©] questionnaire; and,
- 9. Clinical course of COVID-19 as a function of serum 25D concentrations of <50 ng/mL, 50 to 100 ng/mL and >100 ng/mL at Days 7, 14, 21 and 28, defined as the proportion of subjects in each treatment group with a total score of ≤ 5 for the selected five COVID-19 symptoms (trouble breathing, chest congestion, dry or hacking cough, body aches and pains, and chills and shivering) using the FLU-PRO Plus[©] questionnaire.

Endpoint items 3-7 are all based on incidence over the entire 42 day study period.

Once daily (during a 24 hour period starting in the evening before bedtime), subjects will record their ability to perform usual activities and their opinion of overall health status in an electronic diary using FLU-PRO[©] Plus questionnaire.

